#### 11.10.4. Annual Follow-up ( $\pm 45$ Days)

All enrolled subjects implanted with a Lotus Valve must be evaluated at 24, 36, 48, and 60 months after the index procedure. During the annual follow-up, the following assessments must be completed. The REPRISE III eCRFs identify the specific data points to be collected.

- Physical examination including weight and height
- NYHA classification
- Modified Rankin Scale score, which must be performed by a neurology professional or certified personnel (external or internal certification); assessors should be independent (not involved with the care of study subjects).
- Current antiplatelet, anticoagulant (if applicable)
- TTE, including assessment of effective orifice area, peak systolic and mean aortic valve gradient pressure, aortic regurgitation assessment, mitral regurgitation, LVEF, left ventricular end-diastolic and end-systolic diameter, TR jet velocity, and LA volume, per the Echocardiography Core Laboratory procedure guidelines. All TTEs must be forwarded to the Core Laboratory for independent analyses.  
**Note:** TTE must be done for all subjects who have a valve implanted in the aortic position during the index procedure.
- Rotational x-ray angiography performed on subjects who received the Lotus Valve to assess for structural valve frame integrity per the Imaging Core Laboratory procedure guidelines (see study Manual of Operations). It must be forwarded to the Core Laboratory for analysis. If additional imaging is performed (e.g., cardiac CT or MRI scan), data may also be provided for analysis.
- Complete serious adverse event (SAE, SADE, USADE, and CEC events) and device deficiencies assessment (with associated treatment).

- Quality of Life Surveys: Kansas City Cardiomyopathy and SF-12 Quality of Life Questionnaires at 3 years and 5 years

#### **11.10.5. Management of Missed or Late Visits**

Missed or late visits will be recorded as protocol deviations and will be reviewed as such by the Sponsor or designee on a regular basis in accordance with applicable standard operating procedures.

**Note:** An in-person visit is required. If an in-person assessment cannot be performed, follow-up by telephone should be attempted. Subject or subject's physician should provide rationale for why the subject cannot come in for the follow-up visit.

#### **11.10.7. Withdrawal and Replacement of Subjects**

While all efforts will be made to minimize attrition, subjects may withdraw from the study at any time, with or without reason and without prejudice to further treatment. Withdrawn subjects will not undergo any additional study follow-up, nor will they be replaced. The reason for withdrawal will be recorded (if given) in all cases of withdrawal. The investigator may discontinue a subject from participation in the study if the investigator feels that the subject can no longer fully comply with the requirements of the study or if any of the study procedures are deemed potentially harmful to the subject. Data that have already been collected on withdrawn subjects will be retained and used for analysis but no new data will be collected after withdrawal.

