### 7.1. Primary Endpoints

#### 7.1.1. Primary Safety Endpoint

The primary safety endpoint is a composite of all-cause mortality, stroke, life-threatening and major bleeding events, stage 2 or 3 acute kidney injury, or major vascular complications at 30 days. The primary analysis set for the primary safety endpoint is the implanted analysis set.

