### 7.1.2. Primary Effectiveness Endpoint

The primary effectiveness endpoint is a composite of all-cause mortality, disabling stroke, or moderate or greater paravalvular aortic regurgitation (based on core lab assessment) at 1 year. The primary analysis set for the primary effectiveness endpoint is the implanted analysis set.

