## **10.2. *Withdrawal***

All subjects enrolled in the clinical study (including those withdrawn from the clinical study or lost to follow-up) shall be accounted for and documented. If a subject withdraws from the clinical investigation, the reason(s) shall be reported. If such withdrawal is due to problems related to investigational device safety or performance, the investigator shall ask for the subject's permission to follow his/her status/condition outside of the clinical study.

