**Table 11.1-1: Study Event Schedule**

Assessment	Screening a	Baseline	Procedure	Within 1 Day Post-procedure	Prior to Discharge or 7 Days Post-Procedure	30 Days b (±7 Days) Office Visit	6 Months b (±30 Days) Office Visit	12 Months b (±30 Days) Office Visit	24–60 Months b [Annual] (±45 Days) Office Visit
------------	------------------------	----------	-----------	-----------------------------	---	---	---	--	--

Imaging Core Laboratory procedure guidelines (see study Manual of Operations). Results must be forwarded to the CT/X-Ray Core Laboratory for analysis. If additional imaging is performed (e.g., cardiac CT or MRI scan), data may be provided for analysis.

- o: Includes the Kansas City Cardiomyopathy and SF-12 QOL questionnaires. Baseline QOLs should be performed within 30 days prior to the index procedure.
- p: QOL survey at 36 and 60 months.
- q: Procedural cine-angiogram including final post-deployment aortogram of the ascending aorta must be done and sent to the CT/X-Ray Core Laboratory for analysis.
- r: For subjects who received a permanent pacemaker related to the index procedure, pacemaker dependence must be captured at the 30-day and 1-year visits via pacemaker interrogation. Pacemaker interrogation should also include assessment of the percentage of beats where the ventricles are paced.
- s: AEs and ADEs will be monitored and collected from the time of enrollment through 12-month follow-up. For subjects who do not receive the study device, AEs will be monitored through 1-year follow-up.
- t: Information on device deficiencies for the test and the control devices, as well as all SAEs, SADEs, UADEs, USADEs, and CEC events will be monitored and reported to Boston Scientific for all enrolled subjects from the time of enrollment through termination of the study. For subjects who do not receive a study device (test or control), the mentioned events will be monitored through 1 year post-index procedure. Please refer to Section 7.2 for a list of CEC events and Table 26.2-1 for definitions of these events, which specify data required for CEC adjudication. Complaint reporting of any device deficiencies for any commercially available products used should also be carried out using the manufacturer’s processes.

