#### 12.1.2.2. Sample Size Parameters for the Primary Effectiveness Endpoint

##### 12.1.2.2.1 Primary Hypothesis

The sample size calculation for the primary hypothesis of the primary effectiveness endpoint at 1 year is based on the following assumptions.

- Expected Lotus Valve (test) rate = 32%
- Expected CoreValve (control) rate = 32%

- Non-inferiority margin ( $\Delta$ ) = 9.5%
- Test significance level ( $\alpha$ ) = 0.025 (1-sided)
- Test : Control ratio = 2:1
- Power ( $1-\beta$ ) = 80%
- Total number of evaluable subjects = 819
- Expected rate of attrition = 10%

Given the above assumptions, at least 912 randomized subjects (608 Lotus Valve, 304 CoreValve) are needed to account for attrition.

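### Section 11.10.7 ends data collection at withdrawal, on its natural reading also after investigator discontinuation; this can lose ascertainable 1-year deaths and conflicts with the event-reporting rule in Table 11.1-1

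*Combined protocol and SAP*

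**What the plan says.** Section 11.10.7 covers two exits in one paragraph. A subject may withdraw at any time. In addition, "The investigator may discontinue a subject from participation in the study if the investigator feels that the subject can no longer fully comply" with the study requirements, or if a study procedure is judged potentially harmful. On what follows, the section says: "Withdrawn subjects will not undergo any additional study follow-up, nor will they be replaced". Data gathered up to that point are kept and analysed, but "no new data will be collected after withdrawal".

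Other parts of the protocol bear on the same subjects:

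- **Section 10.2.** If withdrawal is due to problems with the investigational device's safety or performance, the investigator asks for "permission to follow his/her status/condition outside of the clinical study". No other reason for withdrawal triggers this, and no route into the trial data is described.
- **Table 11.1-1, footnote t.** Serious adverse events and events for the Clinical Events Committee "will be monitored and reported to Boston Scientific for all enrolled subjects from the time of enrollment through termination of the study". Section 7.2 lists mortality among the adjudicated events. Subjects who never receive a study device are followed for these events for 1 year.
- **Sections 11.10.5 and 11.10.6.** When an in-person visit is impossible, telephone follow-up should be attempted. A subject is not to be declared lost before the 1-year visit, and only after three documented failed attempts to reach the subject or next of kin.
- **Sections 7.1.1 and 7.1.2.** "The primary safety endpoint is a composite of all-cause mortality, stroke" and other events at 30 days. "The primary effectiveness endpoint is a composite of all-cause mortality, disabling stroke" or moderate or greater paravalvular regurgitation at 1 year.
- **Sections 12.1.1.3 and 12.1.2.3.** Sensitivity analyses such as tipping-point are planned for inadequate follow-up in the safety endpoint, and similar procedures apply to effectiveness.

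**The concern.** Death is the one component of the 1-year composite that can be learned without a visit, an echocardiogram or the subject's effort. A rule that closes data collection at withdrawal gives that up. If the rule also covers investigator discontinuation, it applies to subjects who have not refused anything.

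The population is at high or extreme operative risk, and frailty is among the qualifying conditions in Section 9.2. Inability to comply is plausibly related to approaching death or to a disabling stroke, so the missing outcomes may be informative. The decision to discontinue rests on the investigator's judgement, and the protocol describes no masking of site investigators to the valve implanted. If the missing outcomes differ between arms, the non-inferiority comparison is shifted.

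There is also an operational problem. A site that learns of a death after discontinuation is told by footnote t to report it and by Section 11.10.7 that no new data are collected. Sites may resolve this differently.

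**Working it through.** **1. The texts side by side.** The no-new-data sentence speaks of withdrawn subjects; the investigator sentence speaks of discontinuing them. They stand in one paragraph under one heading, and no other follow-up rule for discontinued subjects is given. Treating discontinued subjects as withdrawn is therefore the natural reading, though not an explicit one. Footnote t makes no exception for withdrawal. Section 10.2 does not settle the conflict, because its follow-up lies outside the study.

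**2. Inputs (Section 12.1.2.2.1).** Expected rates 32% and 32%; margin 9.5 points; one-sided alpha 0.025; allocation 2:1; 819 evaluable subjects; "Expected rate of attrition = 10"%; 912 randomized (608 and 304).

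**3. The plan's own figure.** Farrington-Manning, 546 and 273 evaluable. The restricted estimates under the null hypothesis are 35.5% and 26.0%.

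- Standard error under the null: √(0.355×0.645/546 + 0.260×0.740/273) = 0.0335
- Standard error under the alternative: √(0.32×0.68×(1/546 + 1/273)) = 0.0346
- Power: Φ[(0.095 − 1.96×0.0335)/0.0346] = 80.1%, against the stated 80%
- 819/0.90 = 910, against the stated 912

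The sample size reproduces, and nothing here disputes it.

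**4. Room below the margin.** With 10% missing, 608×0.9 ≈ 547 and 304×0.9 ≈ 274 remain. Control is held at 32%, and z = (observed difference − 0.095)/(null standard error).

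- Excess 2.8 points: (0.028 − 0.095)/0.03405 = −1.97, passes
- Excess 3.0 points: (0.030 − 0.095)/0.03409 = −1.91, fails

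The largest observed excess that passes is about 2.8 points.

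**5. Shift from unobserved subjects.** Let a fraction m be missing in each arm, and let g be the Lotus-minus-CoreValve gap in event rate among them. If the observed difference is zero, the full-cohort difference is m×g. The documents do not break down the 10%, so m is an assumption:

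| Assumed m | Shift per 10-point gap | Gap that uses up 2.8 points |
|---|---|---|
| 3% | 0.3 | 2.8/0.03 ≈ 93 points |
| 5% | 0.5 | 2.8/0.05 = 56 points |
| 10% | 1.0 | 2.8/0.10 = 28 points |

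**6. One adverse case.** Assume missing Lotus subjects at 64% and missing CoreValve subjects at 32%. Completers (32% in both arms) give an upper 97.5% bound of about 6.6 points.

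- At m = 10%, the Lotus rate is 0.9×32 + 0.1×64 = 35.2%. The difference is 3.2 points and the bound on 608 and 304 is about 9.55, just above the margin.
- At m = 5%, the Lotus rate is 0.95×32 + 0.05×64 = 33.6%. The difference is 1.6 points and the bound is about 7.9, below the margin.

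**7. The 30-day endpoint.** Section 12.1.1.1 counts a subject who has an event within 30 days or is followed for at least 23 days. Only event-free subjects who leave before day 23 drop out.

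**The case against.** The strongest reply is that the protocol already pursues subjects who cannot attend. Sections 11.10.5 and 11.10.6 require telephone attempts, allow next-of-kin contact and bar an early declaration of loss. This stands. A reader might infer that every frail subject who stops attending vanishes from the data; the documents do not support that. What remains is the subject who is formally withdrawn or discontinued, to whom those sections no longer apply if Section 11.10.7 is followed.

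Second, it can be said that Section 11.10.7 never states that discontinued subjects are withdrawn, and that footnote t demands event reporting for everyone. Both are correct. They show that the text is in conflict; they do not show that deaths will be captured.

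Third, 10% is total attrition for a composite that includes a core-laboratory echocardiogram. A reader might infer that about 91 subjects (10% of 912) would lose vital status through withdrawal. The plan gives no withdrawal share, so 10% is only the top of an assumed range.

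Fourth, tipping-point analyses are planned. They show how far missing outcomes could alter the conclusion, but they do not replace deaths that a telephone call could establish.

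Fifth, the consent form is not in the text reviewed. Permission for status checks may already be there and cannot be treated as absent.

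**Conclusion.** The point holds as a cheap and worthwhile correction. Followed as written, Section 11.10.7 loses deaths that could be ascertained after withdrawal and, on its natural reading, after investigator discontinuation. It also contradicts footnote t, and Section 10.2 does not repair it.

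The effect is mainly on the 1-year composite. A reader might infer that both primary endpoints are equally exposed, since death is in each. The 23-day rule and the retention of earlier events make the 30-day exposure much narrower.

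A reader might also infer that the non-inferiority conclusion is in serious danger. The figures do not support that. From a zero observed difference, the gap between arms among missing subjects would have to be about 28 points if all 10% withdrew, 56 points at 5% and 93 points at 3%. Missingness that is informative to a similar degree in both arms shifts the difference little, and the direction of any shift is unknown. The bias is possible but probably small. This rests on the planned 32% rates, equal missing fractions in the two arms, and the assumed 3% to 10% range.

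**What to change.** - **Section 11.10.7:** distinguish stopping study visits from withdrawing consent to all further data, and say which applies when the investigator discontinues a subject.
- **Data to collect:** for investigator-discontinued subjects, and for withdrawing subjects who agree, obtain vital status to day 365, and stroke status where possible, by telephone, medical records or public death records as consent and local law allow. Include it in the endpoint data. A subject who refuses all contact is left alone.
- **Reconciliation:** bring Section 10.2, footnote t of Table 11.1-1 and Section 11.10.7 into agreement.
- **Analysis text:** state how a subject known to be alive at day 365 without a 1-year echocardiogram is counted, so that recovered deaths do not enter while recovered survivors drop out.
- **Consent form:** align it if it does not already permit this.

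The cost is an amendment, possible consent wording and brief site effort, with no added visit or procedure. Paravalvular regurgitation is not recovered. For that reason the power figures (Farrington-Manning, 912 randomized: 80.2% with 10% missing, 82.2% with 5%, 84.1% with none) overstate the gain; the purpose is to reduce possible bias.

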#### **11.10.8. Explant Procedure**

If a Lotus Valve test device is explanted during conventional scheduled or emergent surgical valve replacement or during an autopsy, if possible, the explanted valve should be sent to an independent histopathology core laboratory for macroscopic and microscopic analyses. Please refer to the study Manual of Operations for recommendations on the explant procedure and shipment of the explanted valve.

If a control device is explanted during conventional scheduled or emergent surgical valve replacement or during an autopsy, please follow the directions in the associated IFU.

Information on the explant procedure must be documented in source notes and captured in the Explant Form of the eCRFs.

### **11.11. Study Completion**

All subjects who receive a test or control device will be evaluated at 30 days, 6 months, 12 months, 24 months, 36 months, 48 months, and 60 months post index procedure. All visits are office visits. A subject's participation in the study will be considered complete after the 60-month visit. For subjects who do not receive a test or control device, participation in the study will be considered complete after the 1-year visit.

### **11.12. Source Documents**

It is preferable that original source documents (see Table 26.2-1 for definition) are maintained, when available. Where copies of the original source document as well as printouts of original electronic source documents are retained, it is recommended that these be signed and dated by a member of the investigation center team with a statement that it is a true reproduction of the original source document.

## **12. Statistical Considerations**

### **12.1. Endpoints**

Data will be summarized separately from subjects in the roll-in (up to 120 subjects with the 23 mm, 25 mm or 27 mm Lotus Valve), randomized, Lotus 21 mm Nested Registry, LOTUS Edge Nested Registry, roll-in with the 29 mm LOTUS Edge Valve (up to 20 subjects), LOTUS Edge 29 mm Nested Registry, and U.S. Continued Access Study populations. Descriptive statistics will be used to summarize the data from subjects in the roll-in, Lotus 21 mm Nested Registry, LOTUS Edge Nested Registry, roll-in with the 29 mm LOTUS Edge, LOTUS Edge 29 mm Nested Registry, and U.S. Continued Access Study cohorts and no statistical inference will be made.

In the randomized cohort, testing of endpoints will be carried out in a hierarchal manner in order to ensure the experiment-wise type I error rate is controlled. Testing will be done in 3 steps with each step needing to reject the null hypothesis in order to proceed to the next step:

1. Test the primary safety endpoint (Section 12.1.1) and the primary hypothesis of the primary effectiveness endpoint (Section 12.1.2.1.1). If the null hypothesis for both endpoints is rejected to show non-inferiority of the Lotus group to the CoreValve group, then proceed to step 2.
2. Test the secondary endpoint (Section 12.1.3); if the null hypothesis is rejected to show superiority of the Lotus group over the CoreValve group, then proceed to step 3.

3. Test the secondary hypothesis of the primary effectiveness endpoint (Section 12.1.2.1.2).

### 12.1.1. Primary Safety Endpoint

The primary safety endpoint is the composite of all-cause mortality, stroke, life-threatening and major bleeding events, stage 2 or 3 acute kidney injury, or major vascular complications evaluated at 30 days after the implant procedure.

#### 12.1.1.1. Statistical Hypothesis for the Primary Safety Endpoint

The statistical hypothesis is that the rate of the primary safety endpoint (composite of all-cause mortality, stroke, life-threatening and major bleeding events, stage 2 or 3 acute kidney injury, or major vascular complications at 30 days) for the Lotus Valve is non-inferior to that for CoreValve.

The primary safety endpoint is expressed as the proportion of subjects who experience mortality, stroke, life-threatening and major bleeding events, stage 2 or 3 acute kidney injury, or major vascular complications within 30 days after the index procedure among all subjects who either experience mortality/stroke/life-threatening or major bleeding events/stage 2 or 3 acute kidney injury/major vascular complications within 30 days after the index procedure or are followed for at least 23 days after the index procedure.

The null and alternative hypotheses for the primary safety endpoint are as follows:

$$H_0: P_{S\_Lotus} \text{ minus } P_{S\_Control} \geq \Delta \text{ (Inferior)}$$

$$H_1: P_{S\_Lotus} \text{ minus } P_{S\_Control} < \Delta \text{ (Non-inferior)}$$

where  $P_{S\_Lotus}$  and  $P_{S\_Control}$  are the rates of the primary safety endpoint at 30 days for the Lotus Valve (test) group and the CoreValve group (control), respectively, and  $\Delta$  (delta) is the non-inferiority margin.

A Farrington-Manning standardized test will be used to test the one-sided hypothesis of noninferiority in the difference between the rates of the two treatment groups, as described in the Statistical Analysis Plan. If the  $P$  value from the Farrington-Manning standardized test is  $<0.025$ , the rate of the primary safety endpoint for the Lotus Valve will be concluded to be non-inferior to the CoreValve rate. This corresponds to the one-sided upper 97.5% confidence bound on the difference between treatment groups (Lotus Valve minus CoreValve) for the observed rate of the primary safety endpoint at 1 year being less than the non-inferiority margin.

#### 12.1.1.2. Sample Size Parameters for the Primary Safety Endpoint

The sample size calculation for the primary safety endpoint is based on the following assumptions.

- Expected Lotus Valve (test) rate = 40%
- Expected CoreValve (control) rate = 40%

- Non-inferiority margin ( $\Delta$ ) = 10.5%
- Test significance level ( $\alpha$ ) = 0.025 (1-sided)
- Test : Control ratio = 2:1
- Expected rate of attrition = 5%

Given enrollment of 912 subjects (608 Lotus Valve, 304 CoreValve) and 5% attrition, there is approximately 85% power to show non-inferiority with the given expected rates.

#### 12.1.1.3. Statistical Methods – Primary Safety Endpoint

All subjects who are enrolled and randomized will be eligible for evaluation. Any events or hospitalizations occurring after enrollment but prior to the index procedure should be entered in the electronic data capture system; events with onset date starting from the time of the index procedure will be included in the primary endpoint analysis.

Handling of dropouts and missing data will depend on their frequency and the nature of the outcome measure. Sensitivity analyses (e.g., tipping-point analysis) will be performed to assess the impact of subjects with inadequate follow-up (i.e., missing data) on the primary endpoint and to assess the robustness of the conclusion of the primary analysis. The sensitivity analysis of the primary endpoint, including events occurring after enrollment but prior to the index procedure, will be performed. Statistical models that account for censored data will be employed in appropriate circumstances (e.g., for time-to-event outcomes). Suspected invalid data will be queried and corrected in the database prior to statistical analysis. Additional information may be found in the Statistical Analysis Plan.

